12.3.3 Secondary Outcomes Measures

12.3.3.1 Secondary Implementation Outcome Measures

The key secondary implementation outcome measure is receipt of ED-initiated BUP. This is a binary outcome and will be defined as the proportion of ED patients receiving ED-initiated BUP amongst ED patients who are candidates for ED-initiated BUP. The outcome will be calculated as a pooled success rate over Post-IF and Maintenance periods.

Other secondary Implementation outcomes will include other measures of reach, including evaluating ED-initiated BUP as a function of time. That is, evaluating the rate of ED-initiated/expedited BUP provided via the ED over the course of the CTN-0079-A1 study with rates of ED-initiated BUP provision estimated secondarily. The outcome measures are: (i) rates of BUP provision between the Post-IF and Maintenance Periods and (ii) diffusion curves in which the number of patients provided BUP is displayed graphically as a function of time.

Other RE-AIM model dimensions to be assessed include: provider adoption measured by the number and proportion of ED providers who have (i) provided BUP treatment and (ii) completed DATA 2000 training to become a BUP prescriber, and Implementation fidelity (proportions for adherence to clinical actions associated with the delivery of ED-initiated BUP). Maintenance will be assessed by evaluating these patient- and setting-level outcomes ≥ 6 months after the cessation of all study-supported IF (i.e., the Maintenance Period).

12.3.3.2 Secondary Effectiveness Outcome Measures

The key secondary effectiveness outcome is linkage to formal addiction treatment for OUD within one week (operationalized at within 7-10 days). This is a binary outcome and will be defined as the proportion of participants with (objectively) confirmed linkage to formal addiction treatment for OUD within one week following ED discharge, amongst participants who received ED-initiated/expedited BUP. The outcome will be calculated as a pooled success rate over Post-IF and Maintenance periods.

Other secondary effectiveness analyses will evaluate the participant subgroups who received ED-initiated BUP and ED-expedited BUP separately as well as those who did not receive BUP.

As in the parent study, a range of secondary effectiveness measures will be assessed at the index ED and Day 30 visits, including but not limited to:

- Self-reported days of opioid and other drug use (TLFB)
- UDS results at 30 days post index ED visit
- Overdose events
- Healthcare utilization
- Quality of Life, Health, and Treatment Effectiveness (PROMIS-29, PHQ-9, TEA)
- Treatment satisfaction and acceptability

Process measures related to the clinical protocol include but are not limited to:

- Proportion of ED patients triaged who are screened for non-medical opioid use
- Proportion of those screened who are positive for non-medical opioid use
- Among those positive:

- Proportion who are candidates to receive ED-initiated BUP
- Proportion who receive ED-initiated BUP (and whether via direct administration, prescription, and/or warm referral within 24 hours)
- Numbers meeting inclusion/exclusion criteria for ED-initiated BUP
 - DSM-5 moderate-to-severe OUD
 - Use opioids in past 7 days
 - Not engaged in medication treatment for OUD
- Proportion who received facilitated referral for treatment amongst those who received some form of ED-initiated BUP.
- Fidelity
 - Critical actions completed

Implementation barriers and facilitators, include:

- Stakeholder acceptability over time (key informant interviews, focus groups)
- ED staff, patient, community barriers and facilitators (key informant interviews, focus groups)

12.4 Statistical Methods for Primary Analyses

Primary and key secondary implementation outcomes analyses will be descriptive in nature, no inferential analysis will be performed. The analyses will examine the overall implementation probabilities (proportions) across the Post-IF and the Maintenance Periods and calculate corresponding 95% confidence intervals. Analyses of the primary and key secondary effectiveness outcomes will follow the approach used for the primary and key secondary implementation outcomes. Each outcome will be presented as an overall effectiveness probability (proportion) across the Post-IF and Maintenance Periods, with a corresponding 95% confidence interval.

12.5 Precision Analyses for Primary Outcomes

We assume that 300 ED patients (150 at each ancillary study period) identified uniformly across the 3 sites will be found to be candidates for ED-initiated BUP. This is the population for the denominator of the primary implementation outcome. We also assume that, of these, approximately 120 participants will get enrolled in the Full Study and become available to evaluate the effectiveness primary outcome. Based on previous assumptions, and data from the parent study, we assume that the true proportion (success rate) of these individuals that actually receive ED-initiated BUP is between 40% to 90%, and the true proportion (success rate) of participants who were engaged in formal addiction treatment for OUD on the 30th day following ED discharge is between 40% to 80%.

12.5.1 Simulation Approach

We investigated the bias and the distribution of the widths of the 95% confidence intervals for the primary implementation outcome measure (i.e., probability of receiving ED-initiated/expedited BUP), and the primary effectiveness outcome measure (i.e., probability of engagement in formal addiction treatment for OUD on the 30th day following ED discharge). The simulations were based on 10,000 iterations assuming the effect of site differences on the outcome measures (site variability) of: $\Delta = (0,0.1,1,2,3)$ and the success rates (p) = $(0.4,0.5,0.6,0.7,0.8,0.9)$ for the

implementation outcome and the success rates (p) = (0.4,0.5,0.6,0.7,0.8) for the effectiveness outcome. We investigated the 95% confidence interval widths for $N=180$, $N=240$ and $N=300$ for the primary implementation outcome and $N=60$, $N=90$ and $N=120$ for the primary effectiveness outcome.

Like the parent study, we use Bayesian estimates for the site-level probability value, assuming beta likelihoods uniform priors to derive posterior moments. That is, if there are S successes and F failures for a site across the Post-IF and Maintenance periods, we take the implementation probability estimate for that site to be $\alpha/(\alpha + \beta)$, with estimated variance $\alpha\beta/[(\alpha + \beta)^2(\alpha + \beta + 1)]$, where $\alpha = S + 1$ and $\beta = F + 1$. We take the overall site success rate estimate to be the average of the three site-level estimates. Because the site-level estimates are independent, the variance of the overall estimate is the sum of the site-level variances divided by 9. To construct confidence limits, we assume the overall estimate is roughly normal in distribution, with upper and lower 95% confidence intervals given by $\pm 1.96 * \sqrt{V_{overall}}$. An exception to this is that we did not allow confidence limits to stray outside (0,1). Same simulation approach was used for primary effectiveness outcome precision analyses.

Simulation SAS code

SAS code to perform this calculation is below. We assume the results of the trial are in file SIMUL, where there is one record per patient, with variables Y, site, and phase, where:

- $y = 1$ if the ED-BUP was implemented for this patient, and 0 otherwise
- $site = 1, 2, \text{ or } 3$, depending on the site of the patient
- $phase = 1$ if the patient was identified during Post-IF period and $phase=2$ if the patient was identified during the Maintenance period.
- The outcome of the calculations is in file EST, where:
- $(e1, e2, e3)$ are the site-specific estimates of the implementation probabilities across Post-IF period and Maintenance period
- $(v1, v2, v3)$ are the estimated variances for $(e1, e2, e3)$
- $(pest)$ is the estimated implementation probability across Post-IF period and Maintenance period
- $(lcest, ucest)$ is the corresponding 2-tailed 95% confidence limit.

```
proc summary nway data = SIMUL;
class site;
var y;
output out = summ sum=;
run;

data summ;
set summ;
heads = y;
tails = _freq_-y;
alpha = heads+1;
beta = tails+1;
e = alpha / (alpha + beta);
v = alpha * beta / ((alpha + beta)**2 * (alpha + beta + 1));
keep heads tails e v;
run;
```

```
%macro t(what);
proc transpose data = summ out = tsumm&what prefix = &what;
  var &what;
  run;
%mend t;

%t(e);
%t(v);

data est;
merge tsumme tsummv;
/* intentional merge without BY statement */
drop _name_;
pest = (e1 + e2 + e3)/3;
vest = 1/9 * (v1 + v2 + v3);
lclest = min (1, max (0, pest - 1.96 * sqrt(vest)));
uclest = max (0, min (1, pest + 1.96 * sqrt(vest)));
ciwidth = uclest - lclest;
run;
```

The same SAS code was used for the primary effectiveness outcome precision analyses.

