Although the rapid timeline of CTN-0079 was of critical import, the brief period of study is not adequate to study the extent to which diffusion of the ED-initiated BUP innovation (clinical program) will occur – as time is a main element of all diffusion research. Most innovations have an S-Shaped rate of adoption with the slope of the “S” varying from innovation to innovation, across different settings, and because of a number of other potential factors.^[7] For example, the curves shown in Figure 1 could represent the rate of adoption of ED-initiated BUP in different EDs and/or when different implementation strategies are employed.

[figure not shown]

Figure 1: From Diffusion of Innovations

Prior to CTN-0079, patients presenting with OUD to its three clinical sites were not offered ED-initiated BUP. In addition to training the staff, policies, documentation templates, referral networks, and other processes needed to be developed and approved prior to implementation. Norms and system-level qualities of each context as well as the opinion leaders within each site – both supporting and opposing the intervention – have differentially impacted diffusion. Throughout implementation, sites have iteratively modified the ED-initiated BUP innovation to be acceptable to the providers and to staff adopters and suit the broader local context. By study close, we anticipate that we will have provided adequate external facilitation for meaningful adoption to take place. However, it is likely that diffusion will be somewhere in the take-off period (Figure 1) by study close, and thus, we will not know the full extent to which adoption will occur. Nor will we be able to report on sustainability or the factors influencing these outcomes.

Building on the existing infrastructure of the CTN-0079 parent study, this ancillary study will evaluate the diffusion and sustainability of the ED-initiated BUP clinical programs introduced through the parent study. This study remains well aligned with our initial **overarching research question:** *In settings with high need, limited resources, and differing staffing structures for managing OUD, what is the feasibility and impact of introducing a clinical protocol for OUD screening and BUP treatment initiation in the ED with referral for treatment?*

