12.3 Primary and Secondary Outcomes Measures

12.3.1 Definition of Primary Implementation Outcome

The primary implementation outcome measure is receipt of ED-initiated/expedited BUP. This is a binary outcome and will be defined as the proportion of ED patients receiving ED-initiated/expedited BUP amongst ED patients who are candidates for ED-initiated BUP. Receipt of ED-initiated/expedited BUP will be operationally defined to include: (1) administration of BUP in the ED, (2) prescription for BUP as part of the ED visit, or (3) provision of a specific “warm” referral or transfer of care to a provider, clinic, or treatment setting with the capacity to administer or prescribe BUP within no more than 24 hours. Data for implementation primary outcome will be abstracted from the health record (EMR abstraction) and/or determined through research staff assessments. The outcome will be calculated as a pooled success rate over Post-IF and Maintenance periods.

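### Does the plan leave the primary proportions without a defined estimator, torn between a patient-pooled rate and an equal-site average?

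*Combined protocol and SAP*

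**What the plan says.** Section 12.3.1 defines the implementation outcome as the "proportion of ED patients receiving ED-initiated/expedited BUP amongst ED patients who are candidates for ED-initiated BUP" and adds: "The outcome will be calculated as a pooled success rate over Post-IF and Maintenance periods". Section 12.3.2 treats 30-day engagement in the same way, among participants who received ED-initiated or ED-expedited buprenorphine. The pooling named is over periods; neither section mentions sites.

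Section 12.4 is the methods section for the primary analyses. It calls them descriptive and says: "The analyses will examine the overall implementation probabilities (proportions) across the Post-IF and the Maintenance Periods and calculate corresponding 95% confidence intervals". It gives no formula and does not point to 12.5.1.

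Section 12.5.1, headed as a simulation approach, follows the parent study in using uniform-prior site posterior means. It then says: "We take the overall site success rate estimate to be the average of the three site-level estimates". The variance is the sum of the three site variances divided by 9, with limits at 1.96 standard errors. The accompanying SAS code says of its input: "We assume the results of the trial are in file SIMUL". Its output *pest* "is the estimated implementation probability across Post-IF period and Maintenance period". Section 12.5 assumes that candidates are "identified uniformly across the 3 sites".

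**The concern.** The text points two ways. Section 12.3 reads most naturally as total successes over total denominator. The only formula on the page is an equal-weight mean of three site rates, and its code is worded as if it were meant for the trial data, with an output described almost as 12.4 describes the primary estimate.

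A patient-pooled rate and a site average answer different questions when large and small sites perform differently. The Introduction says that site norms, system-level qualities and opinion leaders "have differentially impacted diffusion", and 12.5.1 simulates site differences. But the simulation keeps site sizes equal, so it cannot show the two estimators separating. The enrolment limits in 9.4.1.1 act on enrolled participants, not on the candidates who form the implementation denominator.

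In a descriptive study the estimate and its interval are the primary result. If two analysts could report different ones from the same data, the choice might be made after the data are seen.

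**Working it through.** **1. The plan's own precision figures.** Section 12.5.3 puts the 90th percentile of the interval width below 0.2 (implementation) and 0.3 (effectiveness). With equal sites of size n and rates near 0.5, each site's posterior variance is about 0.25/(n+3), and the width is 2 × 1.96 × √[3 × 0.25/(n+3)/9].

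- N = 300 (n = 100): 3.92 × √(0.25/309) = 0.111.
- N = 120 (n = 40): 3.92 × √(0.25/129) = 0.173.

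Simulating the 12.5.1 calculation over all listed rates and sample sizes (the scale of Δ is undefined, so log-odds offsets were assumed) gives largest 90th percentiles of 0.142, 0.124 and 0.111 at N = 180, 240 and 300. For effectiveness they are 0.235, 0.196 and 0.172 at N = 60, 90 and 120. The stated bounds hold. They also hold with unequal sites: the largest values found at the planned sizes were 0.151 (200/75/25) and 0.187 (60/40/20).

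**2. When the two estimators differ.** For site sizes nᵢ and rates pᵢ, pooled rate − site average = cov(nᵢ, pᵢ)/mean(nᵢ). The gap is zero if sizes are equal, if rates are equal, or if the two are uncorrelated. The uniform prior adds a slight pull towards 0.5. With 100 per site and rates of 40/60/90%, the pooled rate is 63.3% and the 12.5.1 estimate is 63.1%.

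**3. Two worked examples.** The documents give no site volumes or rates, so these counts are assumed.

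*75/150, 60/100, 35/50.* Pooled: 170/300 = 56.7% (Wilson 51.0 to 62.2%). By 12.5.1: (76/152 + 61/102 + 36/52)/3 = (0.5000 + 0.5980 + 0.6923)/3 = 59.7%. Variance: (0.001634 + 0.002334 + 0.004019)/9 = 0.000887; interval 53.8 to 65.5%. Identity: covariance [50 × (−0.1) + (−50) × 0.1]/3 = −3.33; divided by 100, −3.3 points.

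*60/150, 60/100, 40/50.* Pooled: 160/300 = 53.3% (Wilson 47.7 to 58.9%). By 12.5.1: 59.6% (54.1 to 65.1%). The gap in raw rates is −6.7 points.

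In both, the rate rises steadily as the site gets smaller, which is one of the two orderings that maximise the gap for those values. Over all six assignments of the rates to the sites, the median absolute gaps are 1.7 and 3.3 points.

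**4. Range of gaps and coverage.** All outcomes of three independent binomials were enumerated at N = 300. Each cell gives the median over the six assignments of rates to sites, with the maximum in brackets, of the absolute gap in points.

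| Site rates | 120/100/80 | 150/100/50 | 180/90/30 |
|---|---|---|---|
| 55/60/65% | 0.3 (0.7) | 0.8 (1.7) | 1.5 (2.5) |
| 50/60/70% | 0.7 (1.3) | 1.7 (3.3) | 3.0 (5.0) |
| 40/60/80% | 1.3 (2.7) | 3.3 (6.7) | 6.0 (10.0) |

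Against the *patient* proportion, the 12.5.1 interval covers less than 90% in 22 of these 54 cases, with a lowest value of 17.5%. Against the quantity it estimates, the *site average*, it covers 94.5 to 95.1% in all 54. The pooled proportion with a Wilson interval covers its own target in 94 to 97%. The low figures therefore measure the distance between two estimands; neither interval fails for its own.

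**5. What depends on the choice.** Section 12.4 excludes inferential analysis of the implementation outcomes and applies the same approach to effectiveness. Section 12.8 again calls the primary analyses descriptive. The interim rule in 5.5 and 12.9 works site by site, and no threshold is set on the overall estimate.

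**The case for a change.** The strongest case for a change is that a methods section should name its estimator, and one sentence in 12.4 would do it. If 12.5.1 is the intended method, 12.4 never adopts it. If it is not, the precision claims were made for an estimator that the trial will not use. Nothing balances the candidate denominator across sites, and in the second example the 12.5.1 interval excludes the observed patient proportion.

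Much of this stands as description. Section 12.4 is silent, and the simulation cannot reveal the difference. But silence here leaves the analyst between two sound options. Following 12.3 and 12.4 as written gives a proportion and a standard binomial interval. Carrying over the parent-study method gives the average success rate of three deliberately different emergency departments, which is a reasonable programme-level summary and consistent with the parent study's method. Preferring the patient-pooled rate to that average is a judgement, since 12.3 does not mention sites.

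The precision argument has little force: with equal sites the two estimates nearly coincide, and the pooled Wald widths at a rate of 0.5 are 0.113 (N = 300) and 0.179 (N = 120), also within the bounds. The effectiveness outcome is less exposed, because 7.2.2 plans about 40 participants per site and 9.4.1.1 limits enrolment by site, although its denominator counts only buprenorphine recipients.

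**Conclusion.** The observation is accurate, but no change follows. Section 12.4 leaves out a detail that an analyst fills sensibly, and the choice between the two fillings is a fair trade-off in a descriptive analysis. The median difference is 0.3 to 6.0 points across the assumed settings at N = 300, at most 1.7 in six of the nine, and 10.0 at the extreme. Gaps of several points need site size and site rate to be correlated together with marked differences in both. These sizes rest wholly on assumed site volumes and rates. Each interval is valid for its own target, the bounds in 12.5.3 hold for both estimators, and no decision uses the overall figure.

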12.5.2 Simulation Results

Below we present the 90th percentile of the distribution of the 95% confidence interval widths and the bias for the implementation and effectiveness probabilities across Post-IF and Maintenance periods. Figures 2-3 present plots for the implementation probability and 3-4 present plots for the effectiveness probability.

[figure not shown]

Figure 2: 90th percentile for the 95% confidence interval widths of the estimate of implementation success rate as a function of the true value (p) for given site variability, Δ and sample size, N .

[figure not shown]

Figure 3: Mean bias for implementation success rate as a function of the true value (p) for given site variability, Δ (Δ) and sample size, N .

[figure not shown]

Figure 4: 90th percentile for the 95% confidence interval widths of the estimate of effectiveness success rate as a function of the true value (p) for given site variability, Δ and sample size, N.

[figure not shown]

Figure 5: Mean bias for effectiveness success rate as a function of the true value (p) for given site variability, Δ and sample size, N .

12.5.3 Summary of Precision Analyses

For all the simulation scenarios investigated for primary implementation and effectiveness outcomes, the 90th percentiles of the 95% confidence interval widths seem to decrease with increase in site differences and are relatively lower for larger sample size; the planned sample sizes of $N=300$ (ED patients) and $N=120$ (participants), but are all below 0.2 and 0.3 for implementation and effectiveness probabilities, respectively. This means for each scenario investigated, 90% of the confidence interval widths are less than 0.2 and 0.3, respectively. The narrow confidence widths imply that, the estimated success rates are good representatives of the true implementation and effectiveness probabilities. There is minor downward bias that seems to diminish with increase in site differences for the implementation probability and effectiveness probability, but the bias is minimal for all the scenarios investigated. In summary, for the planned sample sizes, and for all scenarios investigated, the estimates for the primary implementation and effectiveness outcomes have small bias and capture the true outcomes with high precision.

12.6 Secondary Analysis

Secondary implementation outcomes will be analyzed using descriptive statistics such as proportions, counts/frequencies with 95% confidence intervals and univariate tests like Chi-Square/Fisher exact test t-test and nonparametric tests, where appropriate. Similarly, secondary

effectiveness outcomes will be analyzed using appropriate summary statistics and univariate tests. Statistical models such as Generalized Linear Models (GLM) and Generalized Estimating Equations (GEE) with appropriate distributions and link functions, and Linear Mixed Models (LMM) may be used to analyze some secondary outcome measures where appropriate.

12.7 Tertiary and Exploratory Analysis

These will include (1) evaluating implementation and effectiveness outcomes over the course of the CTN-0079 parent and CTN-0079-A1 ancillary studies and conducting comparisons between each of the defined 6-month Implementation (i.e., parent study), Post-IF, and Maintenance Periods for which comparable data exists; (2) Testing several permutations of the primary implementation and effectiveness outcomes. For example, (i) permutations of how the numerator or denominator are defined and how these data are collected for the primary implementation outcomes (e.g., excluding referrals; including only patients identified through EMR documentation) (ii) permutations to effectiveness outcomes and analyses will include evaluation of linkage and engagement over different timeframes (e.g., linkage within 72 hours, 14 days, and 30 days; time-to-event analyses), evaluating alternative denominators (e.g., including participants who did not receive ED-initiated BUP), and alternate means of how these data are captured and defined (e.g., claims and other administrative data). Other analyses will include comparing the agreement of quality measures assessed using administrative data to the gold standard data collected through the clinical research assessments and identifying patient-level characteristics as well as structural and process measures associated with measure completion and effectiveness. See section 8.3 for more details on tertiary and exploratory outcomes.

Analyses of tertiary and exploratory outcomes may use the same approaches used for primary and secondary outcomes. Additionally, time-to-event analyses may be conducted for linkage and engagement time-to-event outcomes.

